PROTOCOL TITLE:

Neuromodulation augmented cognitive remediation to improve executive dysfunction in fetal alcohol spectrum disorder

PRINCIPAL INVESTIGATOR or FACULTY ADVISOR:

[name]. Department of Psychiatry [contact] [contact]

STUDENT INVESTIGATOR: NA

VERSION NUMBER/DATE:

Version 1: 11-2-2017

REVISION HISTORY

Revision #	Version Date	Summary of Changes	Consent Change?

Table of Contents

1.0	Objectives	4
2.0	Background	4
3.0	Study Endpoints/Events/Outcomes	8
4.0	Study Intervention(s)/Investigational Agent(s)	8
5.0	Procedures Involved	9
6.0	Data and Specimen Banking	. 13
7.0	Sharing of Results with Participants	. 14
8.0	Study Duration	. 14
9.0	Study Population	. 14
10.0	Vulnerable Populations	. 14
11.0	Local Number of Participants	. 15
12.0	Local Recruitment Methods	. 16
13.0	Withdrawal of Participants	. 16
14.0	Risks to Participants	. 17
15.0	Potential Benefits to Participants	. 19
16.0	Data Management	. 19
17.0	Confidentiality	. 19
18.0	Provisions to Monitor the Data to Ensure the Safety of Participants	. 20
19.0	Provisions to Protect the Privacy Interests of Participants	. 20
20.0	Compensation for Research-Related Injury	. 20
21.0	Consent Process	. 20
22.0	Setting	. 21
23.0	Multi-Site Research	. 21
24.0	Resources Available	. 21
25.0	References	. 22

ABBREVIATIONS/DEFINITIONS

- PAE: Prenatal Alcohol Exposure
- FASD: Fetal Alcohol Spectrum Disorders
- MRI: Magnetic Resonance Imaging
- tDCS: Transcranial Direct Current Stimulation

STUDY SUMMARY

Study Title	Neuromodulation augmented cognitive remediation
	to improve executive dysfunction in fetal alcohol
	spectrum disorder
Study Design	Randomized, double-blind, placebo (sham) trial
Primary Objective	Establish feasibility of tDCS for enhancing the
	efficacy of cognitive training in FASD youth.
Secondary Objective(s)	
Research	Transcranial direct current stimulation (tDCS)
Intervention(s)/Investigational	Magnetic Resonance Imaging (MRI)
Agents	
IND/IDE # (if applicable)	N/A
Investigational Drug Services	N/A
# (if applicable)	
Study Population	Children and adolescents with Fetal Alcohol
	Spectrum Disorders
Sample Size (number of	40
participants)	
Study Duration for Individual	4-8 weeks
Participants	

1.0 Objectives

- 1.1 Purpose:
 - Aim 1: Characterize the feasibility and tolerability of combined cognitive remediation and tDCS in children ages 10-16 with FASD.
 - Hypothesis 1: Children with FASD will tolerate the procedures and remain in the study with less than 20% dropout over the course of cognitive remediation and tDCS
 - Aim 2: Evaluate the potential additive benefits of tDCS to the base cognitive remediation program.
 - Hypothesis 2: Cognitive remediation with active tDCS vs. sham tDCS will result in greater gains over the courses of treatment.
 - Aim 3: Examine the brain circuitry changes following the intervention.
 - Resting and task fMRI will demonstrate greater change with active compared with sham tDCS.

2.0 Background

2.1 Significance of Research Question/Purpose:

Prenatal alcohol exposure (PAE) has profound detrimental effects on brain development and, as a result, has permanent consequences for cognition, learning, and behavior. Individuals with Fetal Alcohol Spectrum Disorders (FASD) commonly have a range of neurocognitive impairments that directly lead to practical problems with learning, attention, working memory, task planning/execution, and decision making, among other areas of functioning. Recent data indicate that 2-5% of the U.S. population has FASD (May & Gossage, 2001).

Despite the profound public health burden posed by FASD, there have been very few treatment studies of any sort in this population. Our group conducted the first randomized controlled trials of the nutrient choline as a neurodevelopmental intervention in 2-5 year old children with FASD, in which we demonstrated effects on sequential memory ([name] et al., 2015). For older children, a very different neurodevelopmental target is needed, and we have narrowed our focus to "plasticity" (the brain's ability to adapt) as that target.

Our group has recently shown that neuromodulation - in the form of transcranial direct current stimulation (tDCS) - can enhance the brain's plasticity in order to increase the efficiency and generalization of cognitive remediation training (Nienow, MacDonald, & [name], 2016). This work has been done thus far in schizophrenia, which is also a neurodevelopmental disorder. This approach to intervention has not yet been tested in FASD, a condition in which we know there are brain plasticity abnormalities.

We propose to conduct a first-of-its-kind pilot study to examine the effects of a cognitive remediation training augmented with tDCS in children and adolescents with FASD. Functional magnetic resonance imaging will be collected to provide preliminary data of brain circuitry changes created by this intervention.

2.2 Preliminary Data:

- Engagement of population in clinical trials: The University of Minnesota Fetal Alcohol Spectrum Disorders Clinic (directed by [name]) and Research Program (directed by [name]) evaluates more than 300 children with FASD per year and has recruited 345 participants over the last 6 years (including 84 children ages 2-5 for the choline clinical trial).
- Clinical trial experience: [name] and [name] have both acquired significant experience designing and conducting randomized controlled trials using novel interventions in clinical populations. [name] has completed two small RCTs using a novel nutritional intervention (choline) in children with FASD. [name] has completed two studies using tDCS in patients with schizophrenia (Nienow et al., 2016) and clinical impulsivity (in preparation).
- tDCS and cognitive training: Schizophrenia has been demonstrated to have impaired neuronal plasticity (Kantrowitz et al., 2016). [name] has conducted work testing the use of transcranial direct current stimulation to enhance cognitive training in schizophrenia (Nienow et al., 2016). A design similar to what is being proposed for this study was used; all subjects received cognitive training focused on working memory but were randomized to either active or sham tDCS. Compared with sham tDCS, active tDCS was found to double the effect size of learning on the

trained task and was also found to increase the generalization to untrained tasks.

- The level of stimulation that will be used is between 1.0 to 2.0 mA. This is the range that has been used in other studies of children including a 2014 study of children ages 5 to 12 years with language disorders (Andrade et al., 2014). In that study, no serious adverse events were reported. For some participants tingling, itching, and discomfort were observed in some participants after 10 sessions but these symptoms immediately resolved upon discontinuation of the tDCS. Furthermore, a comprehensive review of pediatric tDCS studies shows that 1.0 to 2.0 mA stimulation consistently produces either no adverse events or mild tingling, itching, and discomfort as described (Antal et al., 2017).
- Cognitive training and imaging: Drs. [name] and [name] have conducted and published multiple neuroimaging studies in FASD ([name] et al., 2006, 2016) so have experience in imaging this population. In a study of cognitive training in schizophrenia, we found that working memory training increased activation of the dorsolateral prefrontal cortex (DLPFC) compared with social skills training. This has provided our rationale for our anode placement over the left DPLFC. In a current study of cognitive training involving executive function (set shifting), we scanned subjects before and after 10 intervention sessions. We found that subjects who received active tDCS had a significant increase in thalamo-frontal activity compared to those with sham tDCS. This demonstrates the ability of the cognitive training with active tDCS to change resting brain circuitry.

2.3 Existing Literature:

Prenatal alcohol exposure disrupts plasticity in the developing brain: A number of pre-clinical studies have demonstrated that neuronal plasticity throughout the brain is affected by PAE. For example, as summarized by Medina, (Medina, 2011), PAE has been shown to disrupt long-term potentiation in the hippocampus (Puglia & Valenzuela, 2010), long-term depression in the hippocampus and cerebellum (Servais et al., 2007), and cortical plasticity in primary visual and somatosensory cortex (Medina, Krahe, & Ramoa, 2005). In animal models, these types of developmental disturbances in

neuronal plasticity contribute to abnormalities in learning, memory, visual processing, and other cognitive functions. In fact, approaches to improve neuronal plasticity have been proposed as interventions (Medina, 2011).

Deficits in plasticity result in significant neuropsychological problems related to executive function: Persons with FASD can manifest a wide variety of behavioral and neuropsychological problems depending on the timing and extent of prenatal alcohol exposure (Mattson, Crocker, & Nguyen, 2011). A common neuropsychological finding is impairments in executive functioning a broad set of skills needed for planning and carrying out of goal directed behavior, including working memory, response inhibition, etc. Impairment in executive functioning has been shown to negatively impact functional outcome in many psychiatric and neurological disorders.

Cognitive training alone has modest effects on working memory in neurodevelopmental disorders:

A common deficit in people with schizophrenia is poor executive functioning in the form of impaired working memory. Medications have not been found to improve executive functioning in schizophrenia. Cognitive training, in which there is repeated drilling of exercises of the impaired function such as working memory, has been shown to improve working memory but with only a modest effect sizes and with considerable subject effort. Another limitation is the limited degree of transfer of improvement from the trained task to untrained task.

Cognitive training alone has modest effects on working memory in FASD: Cognitive training has also been tried in FASD. Kerns et al. (Kerns, Macsween, Vander Wekken, & Gruppuso, 2010) used computer based attention exercises administered by educational assistants, in ten children ages 6-15 years. An average of 16 hours of training was provided over 9 weeks. Significant improvement was noted in several attention measures and there were trend improvements in working memory with effect size of d=0.5. In a study that combined subjects with autism spectrum disorder and FASD (Kerns, Macoun, MacSween, Pei, & Hutchison, 2016), a game designed to target attention and working memory was used in subjects 6-11 years, administered by an educational assistant. Approximately 12 hours of training was provided over a 12 week school period. Significant improvements were noted in attention and working memory. However, since the two groups were merged, the specific effect for those with FASD could not be determined. A

limitation of both of these studies is that neither used a randomized controlled design. The durability of the intervention was also not assessed.

3.0 Study Endpoints/Events/Outcomes

3.1 Primary Endpoint/Event/Outcome:

The primary endpoints will be BrainHQ (Posit Science, San Francisco, CA) task performance measures.

- Learning curves derived from repeated sessions of BrainHQ training will serve as the primary endpoints:
 - Scene Crasher; Mind Bender; Juggle Factor; Eye for Detail; and Divided Attention
- *3.2* Secondary Endpoint(s)/Event(s)/Outcome(s):
 - Neurocognitive measures will be administered at baseline and again after completion of training:
 - Subtests from the Delis-Kaplan Executive Functioning System (DKEFS)
 - Delis Rating of Executive Functioning (D-REF)
 - NIH Toolbox measures (Flanker, Dimensional Card Sort Test, Picture Sequence Memory Test, and Oral Symbol Digit Test)
 - Functional Connectivity analysis of resting-state fMRI data
 - o Seed-based functional connectivity measure
 - Graph theoretical analysis of connectivity

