5.0 Procedures Involved

- 5.1 Study Design:
 - The study will be a randomized, double-blind, placebo (sham) controlled trial.
 - Eligible participants will be randomized to treatment or placebo in a 1:1 allocation ratio (n=20 active tDCS, n=20 sham).
 - Randomization will be from a computer procedure for randomization and tracking.
 - All members of the team will be blinded to assignment.
 - A block randomization procedure with variable block sizes will be used to maximize unpredictability of assignment.
- 5.2 Study Procedures:
 - Intervention (active tDCS vs. sham): There will be a total of 6 visits for the study an initial baseline and intervention visit; four

additional intervention visits and one follow-up visit (within one week of the last intervention session)

- Visit 1: Baseline session; three hour visit.
 - a. Obtain consent; conduct safety screen for MRI (15 min)
 - b. Baseline MRI scan (45 min)
 - c. Baseline cognitive testing (60 min)
 - d. First tDCS intervention session (60 min)
 - i. 14 minutes set-up
 - ii. 46 minutes of cognitive training interleaved with two 13 minute blocks of active or sham tDCS (26 minutes total active/sham tDCS)
- Visits 2-5: tDCS intervention sessions; one hour visits.
 - a. 14 minutes set-up
 - b. 46 minutes of cognitive training interleaved with two 13 minute blocks of active or sham tDCS (26 minutes total active/sham tDCS)
- Visit 6: Follow-up; two hour visit. Within one week of the last intervention session
 - a. Obtain consent/screen for MRI (15 min)
 - b. Repeat MRI scan (45 min)
 - c. Repeat cognitive testing (60 min)
- Cognitive Training Description (Brain HQ):
 - 46 total minutes of cognitive training using the BrainHQ software (Posit Science, San Francisco, CA) will be completed by each subject in each intervention session.
 - The BrainHQ software includes a number of brain training games which focus on various aspects of attention, reaction time, memory and executive function.
 - Positive findings using the BrainHQ program have been reported in children with ADHD (Mishra, Merzenich, & Sagar, 2013) as well as adults with traumatic brain injury (Lebowitz, Dams O'Connor, & Cantor, 2012).
 - The BrainHQ program allows for real-time monitoring of subject performance and adjusts the difficulty level of individual tasks accordingly.

- Additionally, it allows for quantitative tracking of subject performance over time both within and across intervention sessions.
- tDCS Description:

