 - Two 13 minute blocks of active or sham 1.0 to 2.0 mA tDCS will be applied in parallel with cognitive training in each intervention session.
 - A 20 minute block of cognitive training without active or sham tDCS will separate the two 13 minute active or sham tDCS blocks with cognitive training.
 - The sham condition will emulate the sensation of tDCS on the scalp at the beginning and end of each 13 minute stimulation block in order to blind the subject to the intervention type, however, current will not be applied for the remainder of the 13 minute blocks.
 - tDCS will be applied with a StarStim Enobio 8 system (Neuroelectrics, Barcelona, Spain) using a bipolar stimulation montage (anode over the left DLPFC/F3 and cathode over the right orbitofrontal cortex/FP2).
 - The StarStim device allows for double-blinded administration of tDCS/sham stimulation during each session.
- Neuroimaging:
 - Pre- and post-intervention fMRI will be collected to examine resting state connectivity changes and reversal learning task changes.
 - a. Subjects will be scanned at the Center for Magnetic Resonance Research on a Siemens Prisma scanner using Human Connectome Project accelerated imaging (Glasser et al., 2016).
 - b. A high resolution structural scan and a select period of resting-state fMRI (eyes open and eyes closed) will be collected.
 - c. fMRI during a reversal learning task will also be collected. Our group has previously used this task to assess brain function related to cognitive flexibility and executive function.

- Analysis will be done using already published functional connectivity approaches (Haut, [name], & MacDonald, 2010; [name] et al., 2016).
- Assessments: Note that all instruments are to be administered for research purposes (not for clinical diagnostic or treatment purposes). Standard precautions will be implemented to reduce potential frustration and fatigue (frequent breaks, positive feedback about performance, etc.)
 - The following assessments will be administered to the child using the NIH toolbox using an iPad:
 - a. NIH Toolbox Flanker Inhibitory Control and Attention Test measures both a participant's attention and inhibitory control. (Heaton et al., 2014)
 - b. NIH Toolbox Dimensional Card Sort Test (DCCS) is an assessment to measure of cognitive flexibility.
 - c. NIH Toolbox Picture Sequence Memory Test (PSMT) is a measure for use in the assessment of episodic memory.

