16.0 Data Management

- *16.1* Data Analysis Plan: Data analyses will include traditional statistical analyses for group differences in neurocognitive and brain measures with control for confounding variables, multiple comparisons, etc.
- 16.2 Power Analysis: We propose to compare changes in cognition and in brain circuitry between the two intervention arms. With an n=20, alpha 0.05, power of 0.8, we have power to detect an effect size of 0.9.
- *16.3* Data Integrity: Neuroimaging data will be subjected to standard quality control measures (both automated and manual) including measuring and controlling for artefacts. Neurocognitive data will be checked for quality by more than one research staff member.

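### Do the primary BrainHQ learning curves need a fixed summary and a pre-stimulation starting point written into the plan?

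*Combined protocol and SAP*

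**What the plan says.** Section 3.1 makes BrainHQ task performance primary: "Learning curves derived from repeated sessions of BrainHQ training will serve as the primary endpoints", for five named games. It gives no slope, final level, mean, gain or model.

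Section 3.2 treats the secondary tests differently: "Neurocognitive measures will be administered at baseline and again after completion of training". BrainHQ is not among them. Section 5.2 introduces BrainHQ at the last step of Visit 1, "First tDCS intervention session (60 min"), and does not list it at Visit 6. Within a session, "A 20 minute block of cognitive training without active or sham tDCS will separate the two 13 minute active or sham tDCS blocks". Section 5.2 also says that the software tracks performance within sessions as well as across them.

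Hypothesis 2 in section 1.1 expects that active stimulation "will result in greater gains over the courses of treatment". Section 16.1 promises "traditional statistical analyses for group differences in neurocognitive and brain measures with control for confounding variables, multiple comparisons, etc". Section 16.2 states "We propose to compare changes in cognition and in brain circuitry between the two intervention arms", and gives a detectable effect size of 0.9 with n=20, alpha 0.05 and power 0.8.

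The Study Summary gives feasibility as the primary objective, and section 2.1 says "We propose to conduct a first-of-its-kind pilot study to examine the effects of a cognitive remediation training augmented with tDCS". Section 5.1 blinds all team members to assignment.

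**The concern.** A curve cannot be tested until a number or a model is taken from it, and the plan names none for the endpoints it calls primary. If the summary were picked after the unblinded curves had been seen, the false-positive rate per game would exceed 5%, and the multiplicity control promised in 16.1 would not obviously count that choice.

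The second worry is the starting point. The plan speaks of gains and changes, yet the games are never played before assigned stimulation begins. A gain or slope that starts at session 1 removes any part of the tDCS effect already present there; adjusting for session 1 removes some of it. The 0.9 in 16.2 might then seem to overstate what the trial can detect on its primary endpoints. Alternatively, 16.2 might not cover those endpoints at all.

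**Working it through.** **1. The plan's own figure.** Inputs: 20 per arm (5.1), alpha 0.05 and effect size 0.9 (16.2), taken as two-sided. For a two-sample t-test the noncentrality is 0.9 × √(20/2) = 2.85 on 38 df, which gives power 0.792. The normal approximation gives 0.812. The stated 80% reproduces.

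**2. Session timing.** 13 + 20 + 13 = 46 minutes, the whole training time, so no BrainHQ minutes precede assigned stimulation. By the end of session 1, 26 of 5 × 26 = 130 stimulation minutes (20%) have been given. The timing point is correct.

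**3. What 16.2 covers.** It refers to cognition and brain circuitry, and 16.1 to neurocognitive and brain measures. Section 3.2 uses the same pairing for its tests and fMRI, which are measured before stimulation. So 16.2 fits the 3.2 measures at least as well as it fits BrainHQ.

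**4. Is there a loss from 0.9?** Let f be the share of the session-5 arm difference already present in session 1. If 0.9 is redefined as a total session-5 effect in SD-of-change units, the effect left after session 1 is 0.9(1 − f):

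| f | effect left | power |
|---|---|---|
| 0 | 0.90 | 79% |
| 0.11 | 0.80 | 69% |
| 0.20 | 0.72 | 60% |
| 0.35 | 0.585 | 44% |
| 0.60 | 0.36 | 20% |

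The plan never defines 0.9 this way. If 16.2 covers BrainHQ change, that change can only run from session 1, so 0.9 is already what remains and its power stays at 79%. The fall in the table comes from the redefinition.

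**5. Summaries compared on equal terms.** Assumptions (not in the documents): SD 1 at every session, equal correlation ρ between sessions, a session-5 difference of 0.9, and an arm difference 0.9 × [f + (1 − f)(t − 1)/4] at session t. No pre-test covariate is used for any summary. Standardised effects:

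- session-5 level: 0.9
- five-session mean: 0.9 × [(1 + f)/2] / √((1 + 4ρ)/5)
- gain: 0.9(1 − f) / √(2(1 − ρ))
- slope: 0.9 × 2.5(1 − f) / √(10(1 − ρ))
- level adjusted for session 1: 0.9(1 − ρf) / √(1 − ρ²), on 37 df

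For example, the slope at ρ = 0.8 and f = 1/9 is 0.9 × 2.222 / √2 = 1.414, power 99%. The value f = 1/9 (0.11) is linear accrual at session midpoints.

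| ρ | f | level | mean | gain | slope | adjusted |
|---|---|---|---|---|---|---|
| 0.5 | 0.11 | 79% | 51% | 69% | 79% | 86% |
| 0.5 | 0.20 | 79% | 58% | 60% | 70% | 82% |
| 0.5 | 0.60 | 79% | 82% | 20% | 24% | 61% |
| 0.8 | 0.11 | 79% | 39% | 97% | 99% | 99% |
| 0.8 | 0.20 | 79% | 44% | 94% | 98% | 97% |
| 0.8 | 0.60 | 79% | 68% | 42% | 50% | 67% |

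Equal treatment matters. A pre-test covariate correlating 0.5 with each session raises level from 79% to 89%. Giving it to level but not to the session-1-adjusted analysis (86% at ρ = 0.5, f = 0.11) reverses their order. With the covariate in both, they have 89% and 90%.

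No column wins throughout. At ρ = 0.8 and f of 0.11 to 0.20, starting from session 1 helps. It does large harm at f = 0.60, which means 60% of the effect is present when at most 20% of the stimulation has been given.

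**6. False positives.** In a null simulation of 20,000 trials with four summaries (level, mean, slope, session-1-adjusted level), each taken alone rejected in 4.9% to 5.3%. Taking the smallest of the four p-values rejected in 13.7%. That is the rate for deliberate selection after unblinding.

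**The case for a change.** The strongest case for a change is that 3.1 itself calls these endpoints primary, Aim 2 is a comparison of arms, and the remedy is a sentence or two needing no new data. Blinding protects the choice of summary only if the choice is made before unblinding, and no section requires that. Multiplicity control that names no family cannot be shown to cover an unstated choice of summary. On either reading of 16.2 a clarifying sentence would help.

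The textual facts in this stand: no summary is named, no unstimulated BrainHQ value is scheduled, and 16.2 leaves its coverage open. The step from there to a needed change does not. The request is that the sponsor choose something. It offers no method shown to be better than what a competent analyst would choose, and the comparison above shows that none could be recommended without knowing ρ and f. Nothing in the documents suggests selection after unblinding, so 13.7% is a worst case. The tracking of performance within sessions would also let an analyst start a curve at the first trials of session 1, close to unstimulated.

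A short run of each game before stimulation would give a clean starting value. It would also lengthen a Visit 1 that already takes 15 + 45 + 60 + 60 = 180 minutes, and add practice on games whose difficulty adapts. That is a debatable trade-off.

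**Conclusion.** No change follows. The learning-curve summary is undefined and session 1 is under assigned stimulation; confidence in both facts is high. Their consequence is limited. Randomisation makes any one summary fixed in advance a valid comparison under no effect, and the choice between summaries depends on two quantities the documents do not give. The 0.9 in 16.2 reproduces at 79% power, and no loss from it has been shown. The power comparisons rest on the assumed equal correlation, SD and shape of effect, and illustrate only that the choice is a trade-off. For a pilot with a feasibility objective, blinded staff and a stated intention to control multiplicity, choosing the summary and saying how session 1 enters is detail that the analysts can settle before unblinding.
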